13.4 Correlative Studies

Correlative studies for this phase II study are exploratory and will be used for hypothesis generation only.

13.5 Reporting and Exclusions

All patients included in the study must be assessed for toxicity and disease status.

13.6 Unblinding Procedures

The Investigator, the study site personnel, and the subject will remain blinded to each subject's treatment with Ribociclib/Placebo throughout the course of the study.

Access to blinded subject treatment information during the study will be made available to the investigator/limited site personnel, only if identification of the study drug is required for a medical emergency. Medical emergency includes a situation in which the knowledge of the specific blinded treatment will affect the immediate management of the subject/subject's conditions, or when knowledge of previous treatments is required for enrollment in another trial, or as part of managing a serious adverse event.

Investigators should note that emergency unblinding is reserved only for emergency situations where lack of knowledge about the actual study drug treatment interferes with appropriate emergency management. **The occurrence of an SAE or progressive disease should not routinely precipitate the immediate unblinding of the label.**

In the event of a Suspected Unexpected Serious Adverse Reaction (SUSAR) (see Section 8.2.8) related to the blinded treatment, the subject's treatment code will usually be

broken before reporting to health authorities and central ethics committees in an unblinded fashion. In compliance with 21 CFR 312 on the collection and verification of presentation of AE/reaction reports arising from clinical trials on medicinal products for human use, investigators and persons responsible for the ongoing conduct of the study will not usually receive unblinded copies of SUSAR reports, unless unblinded information is judged necessary for safety reasons.

At the end of August 2023, the Placebo drug manufactured and provided by Novartis, expired and an unblinding of the Scenario 2 patients who were on treatment at the time was required. Guidance was provided to all study sites noting that all patients that are Active/On Treatment on scenario 2 will undergo an unblinding process following which patients will continue to receive the assigned treatment: patient who received Ribociclib will continue to do so and patients who received Placebo will continue to receive the endocrine treatment alone, as part of the study. Please note, the study does not allow for crossover between the study groups.

13.6.1 Unblinding requests

If emergency unblinding is necessary for the treatment of a subject, the unblinding should be first approved by the Sponsor-Investigator at least 24 business hours in advance. The request must provide the study ID, date the request is needed, an explanation of the medical need and must be made by the PI/designee.

These requests must be submitted to the study email [contact] between the hours of 9:00 am EST – 5:00 pm EST.

Once the unblinding is processed, the appropriate designee will separately communicate the treatment allocation via email to limited personnel from the site requesting the unblinding. The study team should maintain documentation of the treatment allocation.

Investigators may only unblind subjects under emergency unblinding rules. If a subject is unblinded by the Investigator, they must first discontinue study drugs.

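### Section 13.6 grants code access for immediate management, but section 13.6.1 puts the same request behind 24 business hours' notice; 13.6 also contradicts itself on enrolment in another trial

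*Combined protocol and SAP*

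**What the plan says.** Section 13.6 keeps investigator, site staff and patient blinded, and opens the code only for a medical emergency. It then defines that term in three limbs:

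- "Medical emergency includes a situation in which the knowledge of the specific blinded treatment will affect the immediate management of the subject/subject's conditions";
- "when knowledge of previous treatments is required for enrollment in another trial";
- management of a serious adverse event.

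The next paragraph states that "emergency unblinding is reserved only for emergency situations" in which not knowing the treatment hinders emergency care. It adds that a serious adverse event or progression should not routinely lead to immediate unblinding.

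Section 13.6.1 sets the procedure. For emergency unblinding, "the unblinding should be first approved by the Sponsor-Investigator at least 24 business hours in advance". The request must explain the medical need and go to the study email address "between the hours of 9:00 am EST – 5:00 pm EST". The allocation comes back by email. "Investigators may only unblind subjects under emergency unblinding rules", and "If a subject is unblinded by the Investigator, they must first discontinue study drugs".

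Neither section requires progression status to be on record before the code is released. The primary endpoint is progression-free survival by local assessment (section 1.2.1). Patients who stop ribociclib without radiographic progression are to be scanned until new anti-cancer treatment or death (section 6.5.1).

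**The concern.** There are two problems of different weight.

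The first is the emergency route. Section 13.6 justifies breaking the blind by immediate need. Section 13.6.1 makes the same request wait for an approval interval counted in business hours. A site that follows the written procedure cannot obtain the allocation in the time frame for which access was granted.

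The second is the definition. Once enrolment in another trial counts as an emergency, an elective request and a true emergency share one queue and one set of conditions. Those conditions do not include a recorded progression status. In a trial whose primary endpoint is judged locally, a code released before the last disease assessment could influence that assessment or later follow-up.

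**Working it through.** The plan gives no figure for the delay, so there is none to reproduce. The check compares the passages and works out the wait that section 13.6.1 implies.

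**1. The emergency request, side by side**

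| | Section 13.6 | Section 13.6.1 |
|---|---|---|
| Ground | Knowledge affects immediate management | Unblinding needed to treat the patient |
| Timing | Immediate need | Approval at least 24 business hours ahead |
| Channel | Not stated | Email request, 9 am to 5 pm EST; reply by email |

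The available text describes no out-of-hours contact, site or pharmacy code break, or approval after the event. The code break for unexpected serious reactions in 13.6 serves reporting to authorities, and investigators do not usually receive the unblinded copy.

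**2. The wait**

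Assumptions: business days are Monday to Friday without holidays; requests are taken on those days; approval is given at the moment of submission and the reply is instant. The last two favour the plan. The documents do not define a business hour, so two readings are shown.

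*Reading A: 24 clock hours, weekdays only.*
- Best: need arises Monday 9 am, release Tuesday 9 am = 24 h.
- Worst: need arises Thursday 5 pm. Wait for the window, 16 h; Friday 9 am to midnight, 15 h; weekend, 48 h not counted towards the 24; Monday to 9 am, 9 h. Total 16 + 15 + 48 + 9 = 88 h.
- A need arising Friday 5 pm gives the same total: 64 h until Monday 9 am, plus 24 h = 88 h, so release is Tuesday 9 am.

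*Reading B: 24 hours of an 8-hour day, 24 / 8 = 3 business days.*
- Best: Monday 9 am to Wednesday 5 pm = 2 × 24 + 8 = 56 h.
- Worst: need arises Wednesday 5 pm, request Thursday 9 am, then Thursday, Friday and Monday, release Monday 5 pm = 5 × 24 = 120 h.

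| | Minimum | Mean over 168 hourly start times | Maximum |
|---|---|---|---|
| Reading A | 24 h | about 46 h | 88 h |
| Reading B | 56 h | about 91 h | 120 h |

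The submission window is closed for 168 − 5 × 8 = 128 of 168 hours a week (76%), or for 168 − 7 × 8 = 112 of 168 (67%) if email is taken every day.

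**3. The definition**

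Enrolment in another trial is inside the emergency definition, yet it is not a situation in which ignorance of the arm hinders emergency care. The two paragraphs of 13.6 cannot both hold. Because 13.6.1 leaves investigators only the emergency rules, the other-trial request has nowhere else to go.

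**4. The path to the endpoint**

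The stated order is: stop study drug, then release the code. No step in between requires the latest RECIST status and date to be signed. What remains exposed is the interval from disclosure to the last local assessment, and the follow-up in that interval.

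**5. Who is still affected**

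Sections 10.3 and 13.6 describe the August 2023 unblinding for Scenario 2 patients on treatment. They do not mention randomised Scenario 1 patients, or patients off treatment and not yet progressed. Section 6.2 gives both scenarios the same post-randomisation regimen, so expiry of the placebo makes continued blinded treatment unlikely in either. Scenario 1 treated 27 patients before randomisation and is closed. The procedure remains in the version dated February 1, 2024.

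**The case against.** The strongest reply has four parts.

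*The approval rule is advisory.* Section 13.6.1 says approval should come first, and most dose-modification rows in section 7.3 act on ribociclib/placebo without needing the code. A reader might infer that the blind can never be broken in time; the text does not go that far. But section 13.6 itself recognises cases in which the allocation matters at once, and no quicker route is written for them.

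*Leaving treatment is decided blind.* Study drug must be stopped before disclosure. A patient leaving for another trial would start new therapy, and scanning under 6.5.1 would end, whether or not the code was opened. A reader might infer that such patients are censored in the primary analysis with their arm known. The documents do not support this. They state no censoring rule for new therapy, ask for every effort to follow outcomes after discontinuation (synopsis and 6.2.4), and apply intention to treat (13.1). This part largely stands and confines the bias to a narrow interval.

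*RECIST status is already signed.* The section 10 footnotes require real-time, investigator-signed restaging after scans and confirmation of disease status before each cycle's dispensing, and the calendar schedules end-of-treatment imaging. This narrows the gap. It does not close it, because sign-off is tied to scans and dispensing and not to release of the code. Independent review (11.1.7) is described for responses, while progression is left to local assessment.

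*Events have overtaken the rule.* Placebo expiry leaves few patients to whom it can apply. This stands as to size. It does not settle the matter for off-treatment patients who are still blinded, or for code breaks already made.

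**Conclusion.** The point holds as a contradiction in the procedure. Sections 13.6 and 13.6.1 cannot both be followed for an emergency. The wait is at least 24 hours on any reading, and up to 88 or 120 hours depending on what a business hour means. These maxima rest on a Monday-to-Friday week without holidays, and on approval given at once. Section 13.6 is also inconsistent within itself on enrolment in another trial.

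The statistical consequence is limited. Unblinding before recorded progression is permitted, not directed, and many patients seeking another trial will already have progressed. The remaining risk is that follow-up, or the last local progression assessment, is influenced by the known arm. Its size cannot be computed, because the documents give neither the number of code breaks nor the number of patients still blinded. Going forward, the effect is probably confined to a small group, mainly off treatment. This is worth correcting, but it is not a reason to doubt the primary analysis as planned.

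**What to change.** 1. Reconcile the approval interval and submission hours in 13.6.1 with the immediate access granted in 13.6, and define a business hour if the term is kept. Which rule governs an emergency is for the sponsor and the safety oversight bodies to settle.
2. Take enrolment in another trial out of the emergency definition. Treat it as a separate non-emergency request, with the latest RECIST status and its date signed before the code is released.
3. Log every unblinding with its date, its reason and its timing relative to recorded progression. Include code breaks already made, so that the report can state how many came before progression.

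The cost is a protocol wording change, one added item on the request form, a short log, and whatever code-release arrangement the reconciliation calls for. Sample size and the planned tests are unaffected.

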14. PROTECTION OF HUMAN SUBJECTS

This study is to be conducted in accordance with applicable government regulations and Institutional research policies and procedures. An IND annual report will be submitted to the FDA in accordance with 21.CFR 312.33.

This protocol and any amendments will be submitted to a properly constituted Institutional Review Board (IRB), in agreement with local legal prescriptions, for formal approval of the study conduct. The decision of the IRB concerning the conduct of the study will be made in writing to the investigator and a copy of this decision will be provided to the sponsor before commencement of this study.

All subjects for this study will be provided a consent form describing this study and providing sufficient information for subjects to make an informed decision about their participation in this study. This consent form will be submitted with the protocol for review and approval by the IRB for the study. The formal consent of a subject, using the IRB-approved consent form, must be obtained before that subject is submitted to any study procedure. This consent form must be signed by the subject or legally acceptable surrogate, and the investigator-designated research professional obtaining the consent.

15. CONSENT: LEGAL AUTHORIZED REPRESENTATIVE IF PATIENT WITHOUT CAPACITY

We may enroll individuals with limited decision making capacity on to the protocol. This is not an exclusion criterion in the protocol and there is the prospect of benefit to participants in this study since participation may improve their condition. The principal investigator and co-investigator will be responsible for making an initial assessment as to whether a subject is competent to provide consent. If this is the case, the investigator will obtain an independent assessment of the individual's capacity to provide informed consent by a licensed physician, not otherwise involved in the research study.

The research team will be present to answer all the LAR's questions adequately before they decide to participate and will be given detailed information about the study purpose, procedures, requirements, risks, benefits, and possible alternatives. The research team will be present to answer all the LAR's questions adequately before they decide whether or not to participate. They will sign the consent form on the designated signature line and sign the HIPAA authorization form (unless already embedded into the informed consent document).

Although not expected given the potential subjects to be enrolled who have limited decision making capacity in this study, in the event that a subject regains their capacity to consent; their ability to provide consent will be assessed first by the principal investigator or co-investigator and then by an independent licensed physician and they will then be re-consented.

16. STUDY FINANCES

16.1 Conflict of Interest:

Any investigator who has a conflict of interest with this study (patent ownership, royalties, or financial gain greater than the minimum allowable by their institution, etc.) must have the conflict reviewed by the Columbia University Conflict of Interest Committee with a Committee-sanctioned conflict management plan that has been reviewed and approved prior to participation in this study. All CUMC investigators will follow the University conflict of interest policy.

APPENDIX A: ECOG PERFORMANCE STATUS CRITERIA

ECOG Performance Status Scale		Karnofsky Performance Scale	
Grade	Descriptions	Percent	Description
0	Normal activity. Fully active, able to	100	Normal, no complaints, no

	carry on all pre-disease performance without restriction.		evidence of disease.
		90	Able to carry on normal activity; minor signs or symptoms of disease.
1	Symptoms, but ambulatory. Restricted in physically strenuous activity, but ambulatory and able to carry out work of a light or sedentary nature (e.g., light housework, office work).	80	Normal activity with effort; some signs or symptoms of disease.
		70	Cares for self, unable to carry on normal activity or to do active work.
2	In bed <50% of the time. Ambulatory and capable of all self-care, but unable to carry out any work activities. Up and about more than 50% of waking hours.	60	Requires occasional assistance, but is able to care for most of his/her needs.
		50	Requires considerable assistance and frequent medical care.
3	In bed >50% of the time. Capable of only limited self-care, confined to bed or chair more than 50% of waking hours.	40	Disabled, requires special care and assistance.
		30	Severely disabled, hospitalization indicated. Death not imminent.
4	100% bedridden. Completely disabled. Cannot carry on any self-care. Totally confined to bed or chair.	20	Very sick, hospitalization indicated. Death not imminent.
		10	Moribund, fatal processes progressing rapidly.
5	Dead.	0	Dead.

APPENDIX B: STRONG CYP3A4 AND CYP3A5 INDUCERS AND INHIBITORS

Because the lists of these agents are constantly changing, it is important to regularly consult a frequently-updated list such as Facts and Comparisons or Lexicomp; medical reference texts such as the Physicians’ Desk Reference may also provide this information. The Principal Investigator should be alerted if the subject is taking any agent on these lists. The list below should not be considered a complete list.

List of prohibited medications during study drug treatment

Category	Drug Name
Strong CYP3A4/5 inhibitors	Atazanavir/ritonavir, boceprevir, clarithromycin, cobicistat, conivaptan, danoprevir/ritonavir, darunavir/ritonavir, elvitegravir/ritonavir, grapefruit juice, idelalisib, indinavir, indinavir/ritonavir, itraconazole, ketoconazole, lopinavir/ritonavir, mibefradil, nefazodone, nelfinavir/nelfinavir, ombitasvir/paritaprevir/dasabuvir/ritonavir (VIEKIRA PAK), posaconazole, ritonavir, saquinavir/ritonavir, telaprevir, telithromycin, tipranavir/ritonavir, troleandomycin, voriconazole
Strong CYP3A4/5 inducers	Apalutamide, carbamazepine ³ , enzalutamide, lumacaftor, mitotane, phenobarbital, phenytoin ³ , rifabutin, rifampin (rifampicin) ³ , St. John's wort (hypericum perforatum) ^{2,3}

Category	Drug Name
CYP3A4/5 substrates with NTII	Alfentanil, astemizole, cisapride, cyclosporine, diergotamine (dihydroergotamine), ergotamine, fentanyl, lomitapide ⁵ , lovastatin, nicardipine, nisoldipine, pimozide, quinidine, simvastatin, sirolimus, tacrolimus
Medications with a known risk for QT prolongation ⁴	Amiodarone, anagrelide, arsenic trioxide, astemizole, azithromycin, bepridil chloroquine, cocaine chlorpromazine, cilostazol, ciprofloxacin, cisapride, citalopram, clarithromycin, disopyramide, dofetilide, domperidone, donepezil, dronedarone, droperidol, erythromycin, escitalopram, flecainide, fluconazole, gatifloxacin, grepafloxacin, halofantrine, haloperidol, ibutilide, levofloxacin, levomepromazine, levosulpiride, levomethadyl, mesoridazine methadone, moxifloxacin, ondansetron, oxaliplatin, papaverine HCl (intra-coronary), pentamidine, pimozide, probucol, procainamide, propofol, quinidine, roxithromycin, sevoflurane, sotalol, sparfloxacin, sulpiride, sultopride, terlipressin, terodiline, terfenadine, thioridazine, vandetanib
Herbal preparations/medications or dietary supplements	Herbal preparations/medications or dietary supplements known as strong inducers or inhibitors of CYP3A4/5 or those with a known risk of QT prolongation are prohibited throughout the study. These include, but are not limited to: St. John’s wort, Kava, ephedra (ma huang), ginkgo biloba, dehydroepiandrosterone (DHEA), yohimbe, saw palmetto, black cohosh, and ginseng. Patients should stop using these herbal medications or dietary supplements 7 days prior to first dose of study drug.
Other investigational and antineoplastic therapies	Other investigational therapies must not be used while the patient is on the study. Anticancer therapy (chemotherapy, hormonal therapy, including but not limited to all SERMS [including raloxifene], biologic or radiation therapy [except for palliative radiotherapy as outlined in the protocol], and surgery) other than the study treatments must not be given while the patient is on the study medication. If such agents are required, then the patient must discontinue the study drug.

Category	Drug Name
	
1 NTI = narrow therapeutic index drugs whose exposure-response indicates that increases in their exposure levels by the concomitant use of potent inhibitors may lead to serious safety concerns (e.g., Torsades de Pointes) or drugs which have <2-fold difference in the minimum toxic concentrations and minimum effective concentrations in the blood.
 
2 Herbal product
 
3 P-gp inducer
 
4 The list provided is as of December 2019. Check https://www.crediblemeds.org/healthcare-providers/drug-list for the most updated list.
 
5 Drug has warning for risk of hepatotoxicity. As far as possible, avoid co-administration of QT prolonging drugs or any other drugs with the potential to increase the risk of drug-related QT prolongation (e.g., via a potential DDI that increases the exposure of ribociclib or the exposure of the QT prolonging drug). A definitive list of drugs with a known risk, possible risk, or conditional risk of QT prolongation and/or Torsades de Pointes (TdP) is available online at qtdrugs.org.
 
Source: Novartis PK Sciences Memorandum: Drug-Drug Interactions (DDI) and Co-medication Considerations for Novartis Clinical Trials (January 2018), which is compiled from Indiana University “Clinically Relevant” Flockhart Table™, University of Washington Drug Interaction Database, and FDA Drug Development and Drug Interactions: Table of Substrates, Inhibitors and Inducers.

List of medications to be used with caution during study drug treatment Category	Drug Name
Moderate CYP3A4/5 inhibitors	Aprepitant, amprenavir, asafoetida resin (Ferula asafoetida), cimetidine, crizotinib, diltiazem, faldaprevir, imatinib, isavuconazole, netupitant, nilotinib, tofisopam, Schisandra sphenanthera (nan wu wei zi), verapamil
Moderate CYP3A4/5 inducers	Bosentan, dabrafenib, efavirenz, etravirine, genistein, lopinavir5, modafinil, nafcillin, telotristat
Sensitive CYP3A4/5 substrates1	Alpha-dihydroergocryptine, apixaban, aprepitant, atorvastatin, avanafil, bosutinib, brotizolam, budesonide, buspirone, cannabinoids6, cannabidiol6, cobimetinib, darifenacin, dasatininb, ebastine, eletriptan, eplerenone, everolimus, felodipine, fluticasone, grazoprevir, ibrutnib, isavuconazole, ivabradine, ivacaftor, lumefantrine, lurasidone, maraviroc, midazolam, midostaurin, naloxegol, neratinib, perospirone, quetiapine, ridaforolimus, rivaroxaban, sildenafil, simeprevir, , ticagrelor, tilidine, tolvaptan, triazolam, ulipristal, vardenafil, venetoclax, vicriviroc, voclosporin
BSEP inhibitors	Alectinib, atorvastatin, bromocriptine, candesartan, clobetasol, clofaziminie, dabigatran, dipyridamole, glyburide, grazoprevir, ledipasvir, mifepristone,pioglitazone, reserpine, rifamycin, simeprevir, telmisartan, timcodar, troglitazone, , velpatasvir

Medications that carry a possible risk for QT prolongation ²	Alfuzosin, apomorphine, aripiprazole, arteminol+piperazine , asenapine, atazanavir, atomoxetine, bedaquiline, bendamustine, bortezomib, bosutinib, buprenorphine, cabozantinib, capecitabine, ceritinib, clomipramine, crizotinib, clozapine, cyamemazine (cyamepromazine), dabrafenib, dasatinib, degarilix, delamanid, desipramine, dexmedetomidine, dolasetron, efavirenz, eliglustat, epirubicin, eribulin mesylate, ezogabine (retigabine), famotidine, felbamate, fingolimod, flupentixol, gemifloxacin, granisetron, hydrocodone-ER, iloperidone, imipramine (melipramine), isradipine, ketanserin, lapatinib, lenvatinib, leuprolide, loperamide, lithium, melperone, midostaurin, mifepristone, mirabegron, mirtazapine, moexipril/HCTZ, necitumumab, , nilotinib, norfloxacin, nortriptyline, nusinersen, ofloxacin, olanzapine, osimertinib, oxytocin, paliperidone, palonosetron, panabinostat, pasireotide, pazopanib, perflutren lipid microspheres, perphenazine, pilsicainide, pimavanserin, pipamperone, promethazine, prothipendyl, quetiapine, ranolazine rilpivirine, risperidone, romidepsin, sertindole, sorafenib, sunitinib, tamoxifen, telavancin, tetrabenazine, tipiracil/trifluridine, tizanidine, tolterodine, toremifene, trimipramine, tropisetron, vardenafil, vemurafenib, venlafaxine, vorinostat, ziprasidone
MATE1/2 substrates ³	Acyclovir, cephalexin, cimetidine, fexofenadine, ganciclovir, glycopyrronium, metformin, pindolol, plisicainide, ranitidine, topotecan, varenicline
OCT1/2 substrates ⁴	Amantadine, , carboplatin, cisplatin, cephalexin, cephadrine, ipratropium, lamivudine, linagliptin, metformin, , oxaliplatin, oxybutynin, phenformin, picoplatin, pilsicainide, pindolol, , ranitidine, sorafenib, tropisetron, trospium, umeclidinium, and zidovudine
BCRP substrates	Daunorubicin, dolutegravir, doxorubicin, hematoporphyrin, imatinib, methotrexate, mitoxantrone, pitavastatin, rosuvastatin, irinotecan, ethinyl estradiol, sulfasalazine, sofosbuvir, tenofovir, topotecan, venetoclax

1 Sensitive substrates include drugs whose plasma AUC values have been shown to increase 5-fold or higher when co-administered with a potent inhibitor.

2 The list provided is as of January 2018. Check <https://www.crediblemeds.org/healthcare-providers/drug-list> for the most updated list.

3 MATE1 and MATE2 share considerable substrate specificity.

4 OCT1 and OCT2 share considerable substrate specificity.

5 Lopinavir and atazanavir is prohibited when combined with ritonavir (see Table 14-1)

[figure not shown]

6 Based data that, exposure of cannabidiol (CBD), tetrahydrocannabinol (THC), 11-hydroxy THC, increased by ~2-3 folds when co-administered with ketoconazole (CYP3A4 inhibitor); Stott et al, Springerplus. 2013; 2: 236

Source: Novartis PK Sciences Memorandum: Drug-Drug Interactions (DDI) and Co-medication Considerations for Novartis Clinical Trials (January 2018), which is compiled from Indiana University “Clinically Relevant” Flockhart Table™, University of Washington Drug Interaction Database and FDA Drug Development and Drug Interactions: Table of Substrates, Inhibitors and Inducers.

